3.1 Primary Objective

To evaluate the effectiveness of the BAAN HUG-M intervention in increasing access to and engagement with the intervention activities, and in promoting HIV testing uptake among young men who have sex with men (YMSM) who have never previously been tested for HIV.

3.2 Secondary Objectives

- To evaluate the effect of the intervention on reducing HIV incidence.
- To evaluate the effect of the intervention on reducing the incidence of chlamydia trachomatis and gonorrhea infections.
- To evaluate the effect of the intervention on reducing sexual risk behaviors (e.g., condomless anal intercourse).
- To evaluate linkage to and retention in HIV care among HIV-positive participants, including the proportion with undetectable viral load.
- To evaluate the uptake of pre-exposure prophylaxis (PrEP) among HIV-negative participants.

3.3 Primary Outcome

- **HIV testing uptake:**

Proportion of participants who report having ever tested for HIV during the 24-month follow-up period. Data will be collected from HIV testing records provided by the Ministry of Public Health national database.

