1.1 Overview of the Problem

Thailand is currently experiencing an alarming HIV epidemic among young men who have sex with men (YMSM), particularly those aged 15–29. In Bangkok, HIV prevalence among YMSM aged 18–24 is as high as 31%. The HIV incidence rate in this group is approximately 12%, which is the highest level documented in Asia.^{1,2} These rates far exceed those in high-risk populations in the United States, where even the most at-risk group, Black MSM, has an incidence rate of around 4%.³ Contributing risk factors among Thai YMSM include being paid for sex, having sex at saunas, and living away from family. The HIV prevalence in northeastern provinces like Ubon Ratchathani and Mahasarakham ranges between 10%–25%, which is over ten times higher than the national average. If no effective prevention strategies are implemented, other regions in Thailand may follow the same trajectory as Bangkok.

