3.4 Secondary Outcomes

- **HIV incidence:**

Number of new HIV infections per 100 person-years, based on seroconversion during follow-up, using data from the Ministry of Public Health national HIV database.

- **Incidence of Chlamydia and Gonorrhea infections:**

Number of new chlamydia and gonorrhea infections identified at each follow-up round, based on self-collected urine and anal specimens.

- **Sexual risk behavior:**

Proportion of participants reporting condomless anal intercourse with male partners in the past 6 months, measured via self-reported survey data.

- **Retention in HIV care:**

Proportion of HIV-positive participants who remain engaged in HIV care at months 6, 12, 18, and 24, based on data from the Ministry of Public Health national database.

- **Undetectable viral load:**

Proportion of HIV-positive participants with a viral load of <200 copies/mL at each follow-up round, as reported in the Ministry of Public Health national database.

- **Current PrEP use:**

Proportion of HIV-negative participants who report currently using PrEP at each follow-up round, based on self-reported data.

4. Analysis Populations

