4.1 Intention-to-Treat (ITT) Population

The ITT population will include all participants who completed the baseline assessment and were assigned to either the intervention or control site, regardless of their level of

participation in the intervention activities thereafter. This population will serve as the primary analytic population for evaluating the effectiveness of the intervention, reflecting real-world implementation outcomes.

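### SAP 3.3 and 4.1 keep men diagnosed with HIV before baseline in the primary testing denominator, which conflicts with SAP 3.1 and lets the contrast shift with each city's diagnosed share

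*Combined protocol and SAP*

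**What the plan says.** SAP 3.3 gives the primary outcome as "Proportion of participants who report having ever tested for HIV during the 24-month follow-up period", and adds: "Data will be collected from HIV testing records provided by the Ministry of Public Health national database". No restriction by HIV status or testing history is attached.

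SAP 4.1 sets the population: "The ITT population will include all participants who completed the baseline assessment and were assigned to either the intervention or control site". It continues: "This population will serve as the primary analytic population for evaluating the effectiveness of the intervention".

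SAP 3.1, the primary objective, directs the testing aim at men "who have never previously been tested for HIV". That restriction does not reappear in the outcome definition (3.3), the analysis populations (4), the models (6.2) or the subgroup and sensitivity analyses (7).

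Protocol 2.2 lists no eligibility criterion on HIV status. SAP 3.4 confirms that HIV-positive men are expected, with an outcome defined as "Proportion of HIV-positive participants who remain engaged in HIV care at months 6, 12, 18, and 24". The same section limits the PrEP outcome to HIV-negative men, so the SAP does restrict denominators by status elsewhere.

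On background rates, Protocol 1.1 states: "The HIV prevalence in northeastern provinces like Ubon Ratchathani and Mahasarakham ranges between 10%–25" (per cent). It gives no separate figure for either province. Protocol 1.2 says 12.5% of MSM in Thailand knew their HIV status.

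**The concern.** A man whose diagnosis predates baseline has already completed the step that the primary outcome measures. It is a reasonable inference, though the documents do not say so, that he will rarely have another diagnostic test on record. His score then depends on how SAP 3.3 is read. If only tests during follow-up count, he is a near-certain 'no'. If 'ever tested' is taken at face value, his earlier positive test makes him an automatic 'yes'. The wording allows both readings, because it joins 'report' and 'ever' to a follow-up window and a database source.

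Under either score the intervention cannot change his result. Two consequences follow. With equal diagnosed shares in the two cities, the risk difference and the planned logit odds ratio are pulled towards no effect. With unequal shares, the contrast moves even if the intervention does nothing, in a direction set by the scoring rule. There is one non-randomised city per arm, so nothing in the design balances these shares. The models in SAP 6.2 have terms for arm, time and their interaction only, and SAP 7 lists no analysis by baseline HIV status.

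If the denominator is settled only after data are seen, it could be chosen by result.

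**Working it through.** **What can be reproduced.** The 600 (300 per site) cannot be, because the documents give no alpha, power, control rate or effect size. The awareness figure in Protocol 1.2 can: 50.3% × 24.9% = 12.5%, as stated.

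**Inputs**
- Prevalence 10% to 25% (Protocol 1.1).
- Awareness 12.5% (Protocol 1.2). It describes all MSM in Thailand; applying it to HIV-positive men in these cities is an assumption.
- Testing among undiagnosed men: 50% with no effect, 65% with a true +15 points (assumptions).
- Share diagnosed at baseline, s. Low: 12.5% × 10% = 1.25% and 12.5% × 25% = 3.125%. Middle: half of positive men diagnosed, so 5% and 12.5% (assumption). Upper bound: all diagnosed, so 10% and 25%.
- Out of 300 men, these shares are about 4 and 9 (low), 15 and 37.5 (middle), and 30 and 75 (upper bound).

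**Formulas.** With p the testing rate in undiagnosed men, the observed proportion is p(1 − s) if diagnosed men score 'no', and p(1 − s) + s if they score 'yes'.

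**Unequal shares, 'no' score, intervention city at the higher share**

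| s control v intervention | No true effect | True +15 points |
|---|---|---|
| 1.25% v 3.125% | 0.96875×0.50 − 0.9875×0.50 = −0.9 | 0.96875×0.65 − 0.9875×0.50 = +13.6 |
| 5% v 12.5% | 0.875×0.50 − 0.95×0.50 = −3.75 | 0.875×0.65 − 0.95×0.50 = +9.4 |
| 10% v 25% | 0.75×0.50 − 0.90×0.50 = −7.5 | 0.75×0.65 − 0.90×0.50 = +3.75 |

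Results are in percentage points. Putting the higher share in the control city reverses the shift: 0.90×0.65 − 0.75×0.50 = +21 for a true +15.

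**Same shares, 'yes' score.** At 10% v 25% with no effect: (0.75×0.50 + 0.25) − (0.90×0.50 + 0.10) = 0.625 − 0.55 = +7.5 points. The sign flips.

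**Equal shares, 'no' score.** A true +15 becomes 0.90×15 = +13.5 at s = 10% and 0.75×15 = +11.25 at s = 25%. The odds ratio falls from (0.65/0.35)/(0.50/0.50) = 1.86 to (0.585/0.415)/(0.45/0.55) = 1.72 and (0.4875/0.5125)/(0.375/0.625) = 1.59. The risk ratio stays at 0.65/0.50 = 1.30.

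**Cost in power of excluding diagnosed men.** This uses a two-proportion normal approximation, two-sided 5%, 300 enrolled per site, an assumed 40% v 52% among undiagnosed men, equal shares and a 'no' score. At s = 10%, power is 76.7% with diagnosed men included and 80.1% with them excluded. At s = 25% it is 64.1% and 72.5%. Exclusion does not lose power here, because the men removed carry no signal.

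All of these are simple proportions. They ignore repeated measures and the one-city-per-arm design, and they are not the GEE estimate.

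**The case against.** The strongest reply is that SAP 3.1 already names never-tested men, so no diagnosed man belongs in the analysis. If the SAP were reconciled towards 3.1, the problem would go. That is right, but 3.1 is never carried into the sections an analyst would follow. Nor is never-tested clearly the settled population: Protocol 1.4 aims at testing at least twice a year, which also concerns HIV-negative men who have tested before. The conflict is part of the finding.

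Second, a reader might infer that the contrast shifts with any difference in HIV prevalence between the cities. It does not. The formula contains only the share diagnosed at baseline. Undiagnosed positive men are proper targets for testing, and cities with different prevalence but equal diagnosed shares show no imbalance shift.

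Third, a reader might take −7.5 points as the expected bias. That figure needs every positive man to be diagnosed and the whole 10% to 25% range to separate the two cities, neither of which the documents support. On the awareness figure the shift is under 1 point. That low end is not the expected case either, because the 12.5% describes all MSM nationally. Protocol 2.1.1 also recruits with the help of public hospitals and health agencies, which could raise the diagnosed share.

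Fourth, the documents do not state that a diagnosed man scores 'not tested', so the direction of the shift is open. And a share that is constant over time may load largely on the arm term of the GEE rather than on the interaction. The SAP does not say how the cumulative outcome enters that model. Both points limit what can be claimed about size and sign. Neither makes a diagnosed man informative about uptake.

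**Conclusion.** The point holds in this form. As SAP 3.3 and 4.1 are written, men diagnosed before baseline are in the primary denominator, no rule says how to score them, and this conflicts with SAP 3.1. Their probable fixed response dilutes the risk difference and odds ratio. With the 'no' score and equal shares, it leaves the risk ratio unchanged.

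The size is a range, because neither city's diagnosed share is given. It runs from under 1 point to 7.5 points under no effect, on the assumptions of 50% testing in undiagnosed men and no retesting of diagnosed men. The sign depends on the scoring rule and on which city has the larger share. Confidence is high that the rule is missing and the sections conflict. It is much lower on the amount of harm.

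A reader might conclude that the primary comparison is invalid unless this is changed. The documents do not support that, since the effect could be negligible. This should be fixed before analysis, but it is not a must-fix.

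**What to change.** - Reconcile SAP 3.1 with 3.3 and 4.1 by stating one primary testing population. At a minimum it should exclude men with an HIV diagnosis in the national database on or before their baseline date. Restricting to never-tested men, as in 3.1, also achieves this. If the wider group is chosen, 3.1 must be reworded to match.
- State that only tests dated after baseline count.
- Keep previously diagnosed men in the cohort for the HIV-care and viral load outcomes.
- Report the number excluded per city, and give the all-participant analysis as a sensitivity analysis with its scoring rule stated.

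The cost is mainly wording. Protocol 2.1.2 already plans to extract HIV status, most recent test date and ART start by national ID. Date of diagnosis is not named there, so the extraction should include it or take a status snapshot at baseline. The minimum exclusion makes the primary denominator somewhat smaller. The never-tested option would cut it much more: Protocol 1.2 reports 73.3% never tested at ages 15–19 and 45% at 20–24, so on those figures it would drop about 26.7% and 55% of these age groups.

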1.4 Objective

To evaluate the efficacy of Baan HUG-M in decreasing sexual risk behavior; increasing HIV testing to at least biannually; and increasing prompt, sustained engagement in care among YMSM living with HIV by using a longitudinal cohort of YMSM in Ubon Ratchathani and Mahasarakham

2. Study design and methods of data collection

This study aims to evaluate the effectiveness of the Baan HUG-M intervention, a community-based strategy designed to promote HIV prevention and facilitate access to care among young men who have sex with men (YMSM) aged 15 to 29 years. A longitudinal cohort design is employed across two geographic locations: Ubon Ratchathani (intervention site) and Mahasarakham (control site), with a total sample size of 600 participants (300 per site). The follow-up period spans 24 months, with data collection occurring at five time points: baseline and months 6, 12, 18, and 24.

Data collection comprises self-administered surveys completed via the Qualtrics platform⁷ and self-collected biological specimens, including urine samples and rectal swabs, for chlamydia and gonorrhea testing. All specimens will be transported to and analyzed at the Office of Disease Prevention and Control 10 (ODPC 10), located in Ubon Ratchathani Province. Additionally, study data will be linked to the national HIV database maintained by the Ministry of Public Health. To protect participant confidentiality, no personally identifiable information is collected within the survey. Instead, a Unique Identification Code (UIC) is assigned to each participant to enable secure and systematic linkage of data across multiple sources.

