2.1.2 Data Collection

Data will be collected at five time points: baseline, and months 6, 12, 18, and 24 of follow-up. At each round, participants will complete self-administered surveys using tablets or smartphones via the Qualtrics platform. A Unique Identification Code (UIC) will be used to longitudinally link participant data across time points. The UIC will consist of the first letter of the province name, followed by an underscore, the first two letters of the participant's last name, and the date of birth in the DDMMYYYY format (e.g., P_AB01012025). To minimize entry errors, local research staff will select the UIC from a predefined list using a forced-choice format.

At each follow-up round, participants will self-collect biological specimens, including urine samples and rectal swabs, for chlamydia and gonorrhea testing. All specimens will be transported under temperature-controlled conditions to the Office of Disease Prevention and Control 10 (ODPC 10) in Ubon Ratchathani for laboratory analysis. Prior to specimen collection, participants will watch a standardized instructional video to ensure correct self-collection procedures.

HIV-related clinical data including the date of the most recent HIV test, HIV status, initiation of antiretroviral therapy (ART), treatment continuity, and viral load results will be extracted from the national HIV database maintained by the Ministry of Public Health using the participant's national identification number. Access to this database will be restricted to the principal investigator and the study statistician to ensure data confidentiality. All data will be stored in encrypted and password-protected formats on secure institutional servers.

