2.1.3 Retention and Engagement Strategies

To promote high retention throughout the study period, the research team will implement continuous engagement strategies through digital communication channels, including the LINE application, SMS, and phone calls, as well as peer-led community outreach. The team will maintain regular contact with participants to provide project updates, appointment reminders, and encouragement to take part in each round of data collection. Participants will receive ongoing support throughout their involvement in the study to foster motivation and consistency in completing questionnaires and providing biological specimens. These combined efforts are expected to result in follow-up retention rates of greater than 60% at each follow-up time point.

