5.2 Data Cleaning and Preparation

Following data export from the Qualtrics platform, the research team will perform systematic data cleaning procedures to ensure data quality, consistency, and readiness for analysis. This process will be conducted using STATA⁷ syntax and command scripts to automate checks and corrections.

Key steps in data cleaning will include the detection of outliers and logically inconsistent responses, verification of skip logic compliance, and range checks for numeric variables. Variables that are expected to align conditionally (e.g., responses to dependent questions) will be cross validated for logical coherence.

In preparation for analysis, data from three key sources will be merged and harmonized:

- Self-administered questionnaires (Qualtrics)
- Laboratory-based test results (chlamydia and gonorrhea from self-collected urine and anal specimens)

- HIV-related clinical data (e.g., HIV status, ART access, viral load) from the Ministry of Public Health national HIV database.

To enable accurate data linkage across timepoints and data sources, participants will be assigned a Unique Identification Code (UIC), which comprises parts of the participant's last name and date of birth. Additionally, linkage to the Ministry of Public Health national HIV database will use the participant's 13-digit national ID number alongside the UIC to ensure robust data matching. The UIC will play a central role in aligning participant records across survey rounds, lab results, and national HIV data systems while preserving confidentiality.

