6.2 Primary and Secondary Outcome Analyses

To evaluate the effects of the intervention over time, Generalized Estimating Equations (GEE) with appropriate link functions (e.g., logit for binary outcomes, identity for continuous outcomes) will be used.⁸ The models will include study arm (intervention vs. control), time (follow-up visits), and their interaction term to estimate intervention effects over time. Robust standard errors will be used to account for within-subject correlation. Person-time will be calculated and compared using rate ratios and 95% confidence intervals.

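### SAP 3.3 words the primary outcome as self-report but sources it to the registry, and the plan never says that registry results are kept for men who miss survey rounds

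*Combined protocol and SAP*

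**What the plan says.** SAP 3.3 describes the primary outcome in two adjacent sentences. The first is "Proportion of participants who report having ever tested for HIV during the 24-month follow-up period". The second is "Data will be collected from HIV testing records provided by the Ministry of Public Health national database".

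Protocol 2.1.2 says that "HIV-related clinical data including the date of the most recent HIV test, HIV status" and later treatment and viral load items "will be extracted from the national HIV database maintained by the Ministry of Public Health". SAP 5.2 adds that "linkage to the Ministry of Public Health national HIV database will use the participant's 13-digit national ID number alongside the UIC". Protocol 2.1.1 has a copy of the national ID card taken at enrolment.

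For the analysis, SAP 6.2 gives one GEE specification for primary and secondary outcomes alike: "The models will include study arm (intervention vs. control), time (follow-up visits), and their interaction term to estimate intervention effects over time". Protocol 2.4.2 says the same with follow-up round as the time variable. SAP 5.1 attributes missing data mainly to drop-out and missed visits. It offers multiple imputation or maximum likelihood under MAR, adds pattern-mixture sensitivity analyses, and permits complete-case analysis where missingness is minimal and ignorable. SAP 4.1 makes everyone with a baseline assessment the primary population. Protocol 2.1.3 and SAP section 2 expect "follow-up retention rates of greater than 60% at each follow-up time point".

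**The concern.** A self-reported test and a registry-recorded test are different variables with different missingness. Self-report exists only for rounds a man attends. The registry record is reached through his national ID, so a missed survey does not by itself remove it.

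The plan does not say which pattern of missingness applies to the primary outcome. Two analysts could follow the SAP and reach different primary results: one using the registry for the whole cohort, the other using visit-level data from attenders, with or without imputation. In the second case the result depends on who stays in contact. Men who stay in touch with a project that promotes testing may be more likely to test, and this tendency may be stronger in the intervention city. That would bias the contrast and lose precision, or it would replace recorded results with values imputed under MAR.

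**Working it through.** **Reading the text.** SAP 3.4 shows how the SAP uses the verb *report* when it describes participants. It appears for condomless anal intercourse and for current PrEP use, and both are sourced to self-reported data. HIV incidence, retention in care and viral load are sourced to the Ministry database, and none is defined by what participants report. Only the primary outcome combines the two. SAP 6.2 and 5.1 do not separate registry variables from survey variables. SAP 4.1 disregards the level of participation in intervention activities, but it does not say how a man with no follow-up survey contributes an outcome.

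**Inputs.** From the documents: 300 men per city, four follow-up rounds, retention above 60% at each. Assumed: a testing proportion of 50% in each city (30% to 70% as a range), independent men, and a Wald interval for a difference of two proportions. The documents give no power calculation, so there is no planned figure to reproduce beyond 300 + 300 = 600.

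**Precision.** Half-width = 1.96 × √(2p(1−p)/n).

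- Registry outcome for all, n = 300, p = 0.5: 1.96 × √(0.5/300) = 8.0 points.
- Attenders at one round at the floor, n = 0.6 × 300 = 180: 1.96 × √(0.5/180) = 10.3 points. The ratio is √(300/180) = 1.29.
- With p = 0.3 or 0.7, the figures are 7.3 and 9.5 points.
- Any attended round counts, with attendance independent across the four rounds (assumed): 1 − 0.4⁴ = 0.974, or about 292 men per city, and 1.96 × √(0.5/292) = 8.1 points.

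The precision cost at p = 0.5 therefore runs from almost nothing (8.1) to 29% (10.3). If the same men tend to miss successive rounds, the figure lies between these.

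**Bias, as illustration only.** Suppose 50% test in both cities, so there is no effect. In the intervention city, assume 70% of tested and 55% of untested men are retained; in the control city, retention does not depend on testing. Among intervention attenders the tested share is 0.5 × 0.70 / (0.5 × 0.70 + 0.5 × 0.55) = 0.35/0.625 = 56%, against 50% in controls. Retention in the intervention city would be 62.5%, within the plan's expectation.

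**Test dates.** The only testing item that protocol 2.1.2 lists is the date of the most recent test. If the extraction falls after a man's month 24, a later test can hide one inside the window. Recruitment runs for one year (protocol 2.1.1), so month 24 falls on different dates for different men. One late extraction of the latest date would not recover the outcome for all of them.

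**The case against.** The strongest reply is that the source is named. SAP 3.3 points to registry records, nothing gives the survey as the source for this outcome, and *report* may be one loose verb. Follow-up visits in SAP 6.2 need not be an attendance rule: SAP 3.4 places retention in care, another registry outcome, at months 6, 12, 18 and 24. SAP 5.1 restricts complete-case analysis to minimal, ignorable missingness, which 40% is not, and it plans pattern-mixture analyses. A linked registry result is not a missing value at all.

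Much of this stands. A reader might infer that the plan excludes men lost to the survey; it does not say so. A reader might also infer that the registry outcome is never missing and that using it costs nothing. The documents do not support that either: they do not state linkage success, registry completeness, or what happens to linkage after withdrawal. The 180-per-city figure is a worst case. In addition, SAP 3.1 directs the testing objective at men never previously tested. If that governs the denominator, both 300 and 180 would change, although the ratio of 1.29 would hold at the same retention.

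The reply does not remove the gap. No sentence says that registry values are kept for non-attenders, and the visit-indexed model does not identify which contrast answers a single 24-month question.

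**Conclusion.** The concern holds as an inconsistency in the primary outcome definition that leaves an attendance-limited analysis open. It does not show that such an analysis is planned or that bias will occur.

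At an assumed 50% testing rate, the precision cost ranges from negligible (8.1 against 8.0 points) to 29% (10.3 points). The upper end requires analysing only attenders at one round at the 60% floor; the lower end requires independent attendance and counting any attended round. The 56% v 50% example rests entirely on assumed differential retention and shows only that the bias can arise within the expected retention. The case for change does not depend on these figures: it concerns the primary outcome, and the linkage needed to settle it is already planned.

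**What to change.** - **SAP 3.3:** define the outcome as at least one HIV test recorded in the national database between enrolment and month 24. Ascertain it by national ID for every linkable ITT participant, whatever his survey attendance.
- **Protocol 2.1.2:** extract all test dates in that window, or time the extraction to each man's month 24.
- **SAP 6.2:** name the single 24-month between-site contrast as primary for this outcome.
- **SAP 5.1:** for this outcome, limit imputation to men who cannot be linked or who withdrew consent to linkage.
- **SAP 7.2:** add self-reported testing as a sensitivity analysis.

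The cost is mainly SAP wording, plus a fuller or better-timed data request on the existing linkage. There is a small downside: tests that the registry does not record are missed in the main analysis, and the documents do not say how complete the registry is. The self-report analysis gives a partial check on this among attenders.
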